9.2 Database design and creation

Construction of the eCRF database in the Medidata Rave system by the CRO Data Department shall comply with FDA 21 CFR Part 11. Data traces such as system entry, data entry, modification, or deletion should be managed in the database, and the establishment of the database should adopt the Clinical Data Exchange Standards Association (CDISC) standard.

9.3 Data Entry

Information shall be entered into the EDC database by the Investigator or the site staff authorized by the Investigator as soon as possible after the completion of the visit, and the data entry shall be carried out in strict accordance with the principle of "what you see is what you record". After the original data is entered, any changes made to the eCRF are automatically recorded in the system.

9.4 Data verification

Based on the finalized data verification plan, the data manager will set up a data logic verification process in the EDC system.

Once the data are entered into the EDC system, if there is any illogical data, the system verification will kick in and trigger a query. These queries will need to be reviewed and answered by the investigator or site staff authorized by the investigator. When updated data make logical checks no longer valid, the data query is immediately closed; if the clinical center confirms the data and provides a response, the data manager is required to review the response information. When justified, the data query is closed; when the data issue is not resolved, the data administrator can continue to communicate with the clinical center by adding data queries until they are finally resolved.

Subject data lists/reports are programmed to be generated to support manual data verification throughout the study. Manual challenges can be added to the EDC system when data arises that requires clarification/verification/confirmation by the investigator. Before locking the database, the data manager confirms that all queries have been resolved and the investigator completes an electronic signature in the EDC system to ensure the integrity and accuracy of the subject data in the EDC system.

9.5 Medical coding

The Data Manager of the CRO Data Department is responsible for the medical coding of this study. Coding will include past medical history, concomitant medication and AE.

Medical history and AE will be coded according to the MedDRA dictionary (version 20.1 or above), and concomitant medications will be coded using the World Health Organization Drug Dictionary (WHO DD), and the dictionaries used will be the versions confirmed by the sponsor.

During the coding process, any data issues that could not be coded due to inappropriate, inaccurate, or ambiguous provision of medical terminology would be requested by the data manager to be verified and confirmed by the investigator in the form of a data query.

Prior to database lock, the data manager sends a medical coding report to the sponsor and is required to be reviewed by the sponsor.

10. Statistical Considerations

10.1 General Principles

A statistical analysis plan will be developed by the biostatistician and principal investigator based on the study protocol, refined and documented prior to the first database lock. Detailed statistical analysis methods will also be specified in the statistical analysis plan.

All statistical analyses will be completed using SAS version 9.4 or above.

Continuous variables will be described by calculating the total number of cases, missing values, mean, standard deviation, median, first quartile, third quartile, minimum, and maximum values.

Categorical variables are described using frequencies and percentages for each category. If required, 95% confidence intervals (95% CI) for frequencies and percentages are calculated.

10.2 Sample size determination

This study is an open, single-arm trial with the purpose of bridging Chinese cGVHD patients to the US registry study (KD025-213) to assess whether BN101/belumosudil treatment of Chinese versus Caucasian cGVHD patients is concordant in terms of efficacy, safety, and PK characteristics, the sample size of the trial is not determined by statistical assumptions.

This study is planned to enroll 30 patients with cGVHD who have undergone at least 1 but not more than 5 lines of systemic therapy, and such a sample size is considered to be sufficient to meet the needs of assessment with the purpose of bridging.

10.3 Statistical Analysis Population

Modified Intent to Treat (mITT): all subjects enrolled and having used at least one dose of study drug.

Per Protocol Set (PPS): The PPS was a subset of the mITT, and included all subjects who have used the study drug after enrollment and have had at least 1 post-treatment efficacy assessment, as well as no major protocol deviations. The exact definition of a major protocol deviation and the inclusion criteria for the PPS were finally determined in the data review meeting.

Safety Set (SS): All subjects who had used the study drug after enrollment and had at least 1 safety assessment.

Pharmacokinetic analysis Set (PKS): all subjects who have used the study drug since enrollment and have post-administration PK data.

Demographic and baseline characteristics of subjects were statistically analyzed based on mITT. mITT was the primary analysis population for the primary efficacy endpoint and PPS was the secondary analysis population. Safety analysis based on SS and PK analysis based on PKS.

10.4 Subgroup Analyses

Subgroup analyses will be conducted for the following subgroups:

- Severe cGVHD (Yes / No)
- Number of organs involved ($<4/\ge4$)
- Number of prior lines of therapy $(1 \text{ vs. } \ge 2)$
- Duration of cGVHD before enrolment (i.e., from time of cGVHD diagnosis to time of enrolment)
- Lung involvement (Yes / No)
- Prior ruxolitinib (Yes / No)
- Prior ibrutinib (Yes / No)

10.5 Data Analysis

Database lock and primary analyses are planned to occur approximately 2 to 3 months after the last subject is enrolled to complete 6 cycles of study medication. All subjects will continue to be followed up for an additional 6 months after the primary analysis as required by the protocol, i.e., the study will end 12 months after enrollment of the last subject, and a follow-up analysis will be performed at the end of the study.

10.6 Statistical Analysis Methods

10.6.1 Distribution of subjects and baseline characterization

Information on subjects who failed screening was tabulated, with the list including screening number and screening failure reason. Screening failure subjects were summarized, including the number of screening cases, the number of screening failures, and the percentage of various screening failure reasons.

Demographic information and baseline metrics will be analyzed based on mITT. Descriptive statistics will be performed for all demographic information and baseline characteristics (e.g., gender, age, ethnicity, height, weight, past medical history, transplantation history, history of GVHD, history of treatment for cGVHD, cGVHD severity, etc.)

10.6.2 Efficacy Analyses

10.6.2.1 Primary Efficacy Endpoint

The primary efficacy endpoint is the ORR, defined as the proportion of subjects evaluated as CR or PR according to the NIH Consensus Criteria (2014) at any one post-baseline assessment. Point estimates and 95% CIs for ORR will be calculated. The 95% CI for ORR is calculated based on the binomial distribution exact probability method.

ORR is calculated based on mITT and PPS, with mITT as the primary analytic outcome.

10.6.2.2 Secondary Efficacy Endpoints

Secondary endpoints are as follows:

- DoR, defined as the time from the first evaluation of CR or PR to the confirmed occurrence of cGVHD progression. For subjects who had not experienced cGVHD progression at the end of the study, the date of their last objective evaluation was used as the DoR censoring date.
- Changes in the Lee Symptom Scale Score: Analyses will include:
 - Number of subjects with a \geq 7 point reduction
 - Number of subjects with a \geq 7 point reduction on 2 consecutive assessments
 - Duration of a \geq 7 point reduction
- Response by organ system: The response assessment for the nine individual organs (Skin, Eyes, Mouth, Esophagus, Upper GI, Lower GI, Liver, Lungs, and Joints and fascia).
- Number and percentage of subjects who have a best response of PR and number and percentage of subjects who have a best response of CR.
- Change in corticosteroid dose
- The prednisone equivalent dose of corticosteroids (mg/kg/day) during the study will be analyzed.
- Change in calcineurin inhibitor dose.
- FFS, FFS is defined as the absence of cGVHD treatment change, non-relapse mortality and recurrent malignancy. Median FFS (from first dose of BN101/Belumosudil) and landmark FFS at 1 year(if applicable) will be analyzed.
- OS, defined as time from first dose of BN101/belumosudil to the date of death due to any
 cause.
- Changes in cGVHD global severity rating using the Clinician-Reported Global cGVHD Activity Assessment
- Changes in symptom activity using the cGVHD Activity Assessment Patient Self-Report

Descriptive statistics will be provided for all secondary endpoints.

For DoR (only for subjects determined to have CR and/or PR), FFS, and OS, the median, first quartile, third quartile, and their two-sided 95% CIs were calculated using the Kaplan-Meier method, and survival curves were plotted.

10.6.2.3 Exploratory efficacy endpoints

Descriptive statistics of changes in PROMIS Physical Mental Functioning Global Health Score.

10.6.3 Safety Analyses

Treatment exposure will be summarized.

For vital signs (including temperature, respiratory rate, sitting blood pressure, and pulse), and physical examination, describe post-treatment changes relative to baseline.

Descriptive statistics of laboratory test abnormalities will be indexed and presented in a cross-tabular format to show the change in laboratory test results of severity \geq 3 (per NCI CTCAE v5.0) pre- and post-treatment with study medications.

For 12-lead ECGs, changes in mean and maximum QTcB and QTcF values relative to baseline will be calculated.

Each type of AE occurring during the study was coded using MedDRA (version 20.1 or above), frequency summarized according to system organ classification, preferred terminology, and frequency summarized and tabulated for AEs of different severity according to the highest level of severity (grades 1-5 according to NCI CTCAE v5.0) and relevance to the study drug. Count the number of subjects who experienced each type of AE, regardless of the number of AEs reported per subject. Descriptively summarize AEs, SAEs, AEs of severity ≥ grade 3 (according to NCI CTCAE v5.0), AEs leading to withdrawal from the study, AEs leading to discontinuation of study treatment, AEs leading to dose adjustments of the study medication, and correlation with the study medication for each of the above types of AEs/SAEs. List of subjects with each type of AE/SAE and death.

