5.5. Treatment Compliance and Exposure

The extent of BN101/belumosudil exposure will be assessed using the duration of BN101/belumosudil treatment.

Duration of treatment (days) = last dose date – first dose date + 1 regardless of unplanned intermittent discontinuations.

The cumulative duration of treatment will be provided, defined as the sum of the duration of treatment for all patients, and will be expressed in patient years.

The relative dose intensity (RDI) will be presented. The RDI is defined as:

$$\text{RDI (\%)} = 100\% * \text{ADI (mg/day)} / \text{PDI (mg/day)} .$$

Where ADI and PDI are the actual dose intensity and planned dose intensity, respectively::

$$\text{ADI (mg/day)} = \text{actual cumulative dose (mg)} / \text{duration of treatment (days)}$$

$$\text{PDI (mg/day)} = \text{planned cumulative dose (mg)} / \text{duration of treatment (days)}$$

The planned cumulative dose is the planned daily dose * duration of treatment, while the actual cumulative dose is the sum of actual doses received over the duration of treatment. The actual total dose will incorporate information of dose reduction and dose interruptions captured in the CRF.

6. Statistical Hypothesis

Since this study intend to evaluate the consistency of the efficacy, safety and PK profile of belumosudil between Chinese cGVHD patients and Caucasian cGVHD patients for the purpose of bridging the results of KD025-213 study, no formal hypothesis testing will be performed. All statistical analyses will be descriptive.

7. Analysis Population

Modified Intent-to-treat (mITT)

mITT: The primary population for efficacy analyses will be a modified Intent to treat (mITT) population defined as all enrolled patients who receive at least one dose of study medication.

The mITT population will be used for tables of demography, baseline characteristics and efficacy.

Responder: The responder population is defined as patients in the mITT population that achieved a partial or complete response at any post-baseline response assessment.

Nonresponder: The nonresponder population is defined as anyone in mITT population that is not a responder.

The responder and nonresponder populations will be used for some subgroup analyses.

Safety Set (SS)

The safety population is defined as all enrolled patients who receive at least one dose of study medication and have at least one post-baseline safety assessment. Safety population will be used for all safety analyses.

Per-protocol Set (PPS)

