8.5.1. Adverse Events

AEs will be coded using the Medical Dictionary for Regulatory Activities (MedDRA) dictionary (Version 25.0 or higher). All AEs (including SAEs) will be graded using the National Cancer Institute (NCI) Common Terminology Criteria for Adverse Events (CTCAE) version 5.0.

Summary of overall treatment emergent adverse events will be tabulated. The subject incidence of the following TEAEs will be presented: any TEAEs, any TEAEs with worst severity, treatment related TEAEs, serious TEAEs, treatment related serious TEAE, \geq grade 3 TEAEs, \geq grade 3 treatment related TEAEs, \geq grade 3 serious TEAEs, \geq grade 3 serious treatment related TEAEs, TEAEs leading to dose interruption, TEAEs leading to dose reduction, TEAEs leading to treatment discontinuation, and TEAEs leading to death.

Following TEAEs will be tabulated by System Organ Class (SOC) and Preferred Term (PT): all TEAEs, serious TEAEs, \geq grade 3 TEAEs, treatment related TEAEs, \geq grade 3 treatment related TEAEs, and serious treatment related TEAEs. Patient will be counted only once within a SOC and PT.

Following TEAEs will be tabulated by PT: all TEAEs, treatment related TEAEs, serious TEAEs, serious treatment related TEAEs, TEAEs leading to dose reduction, treatment related TEAEs leading to dose reduction, TEAEs leading to dose interruption, treatment related TEAEs leading to dose interruption, TEAEs leading to treatment discontinuation, treatment related TEAEs leading to treatment discontinuation, \geq grade 3 TEAEs, \geq grade 3 treatment related TEAEs, CMQ bacterial infection, CMQ viral infection, CMQ fungal infection, CMQ cytopenia, SMQ liver related investigations, signs and symptoms, SMQ drug related hepatic disorders – comprehensive search (narrow), \geq grade 3 CMQ bacterial infection, \geq grade 3 CMQ viral infection, \geq grade 3 CMQ fungal infection, \geq grade 3 CMQ cytopenia, \geq grade 3 SMQ liver related investigations, signs and symptoms, and \geq grade 3 SMQ drug related hepatic disorders – comprehensive search (narrow). Patient will be counted only once within a PT.

Subject listings will be provided for AEs, SAEs, AEs leading to dose interruption, AEs leading to dose reduction, AEs leading to treatment discontinuation, and deaths.

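### Adverse events are planned only as crude subject percentages under open-ended treatment; add time-at-risk and fixed-window summaries to support the safety consistency statement

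*Protocol*

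**What the plan says.** Protocol 10.6.3 sets the counting rule: "Count the number of subjects who experienced each type of AE, regardless of the number of AEs reported per subject". SAP 8.5.1 follows it: "The subject incidence of the following TEAEs will be presented", with each patient counted once within a system organ class and preferred term. Neither document plans an AE rate per unit of time, a time-to-first-AE estimate or a common fixed AE window.

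The purpose is comparative. Protocol 10.2 says the trial is "to assess whether BN101/belumosudil treatment of Chinese versus Caucasian cGVHD patients is concordant in terms of efficacy, safety, and PK characteristics", bridging to KD025-213. SAP section 6 says it is to "evaluate the consistency of the efficacy, safety and PK profile of belumosudil between Chinese cGVHD patients and Caucasian cGVHD patients", and adds: "All statistical analyses will be descriptive".

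Exposure is summarised separately. SAP 5.5 states: "The cumulative duration of treatment will be provided, defined as the sum of the duration of treatment for all patients", in patient-years. SAP 8.3.8 adds categories for duration of treatment and of follow-up, and dose intensity. None of this is linked to the AE tables.

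**The concern.** A crude percentage counts everyone who has had at least one event by the data cut. For any event that keeps occurring on treatment, it rises with time on drug even when the underlying risk is constant. This trial has two cuts with different exposure by design, and it is meant to support a statement about safety relative to another study. If time on drug differs between the data sets being read side by side, the one with longer exposure looks less safe. The planned AE tables could neither show nor correct this. The plan uses time-based methods for response duration, failure-free survival, overall survival and time to next therapy, but none for AEs.

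**Working it through.** **Inputs from the documents**
- Enrolment of about 6 months; cuts at 6 and 12 months after the last patient is enrolled (SAP section 4; Protocol 3.5).
- Treatment continues until progression, toxicity, new therapy and similar events (Protocol 3.3). AEs are collected to 28 ± 7 days after the last dose or until new systemic therapy, whichever is first (Protocol 8.6.2.1).
- KD025-213 results are quoted at 6 months after its last enrolment (Protocol 1.4.2). Its treatment duration and accrual length are not given.
- Overseas AE percentages: Protocol Table 1.

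**Table 1 reproduced.** For cGVHD at 200 mg QD, N = 83: any TEAE 82/83 = 98.8%, diarrhoea 27/83 = 32.5%, upper respiratory tract infection 24/83 = 28.9%, pneumonia 9/83 = 10.8%. All match. The denominator equals 17 (KD025-208 cohort 1) + 66 (KD025-213 200 mg QD) = 83, so these are crude percentages pooled over two studies.

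**Between this trial's two cuts.** Maximum exposure is 6 to 12 months at the primary cut (mean 9.0) and 12 to 18 months at the follow-up cut (mean 15.0).

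Assumptions: uniform enrolment; constant AE hazard λ = −ln(0.70)/6 = 0.0594 per month, so that 30% have the event by 6 months of continuous exposure; exponential discontinuation at rate d = ln(2)/median; events counted while on drug. The documents do not give time on drug, so the median is varied.

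Crude incidence is the mean, over follow-up u, of λ/(λ+d) × [1 − exp(−(λ+d)u)].

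| Assumed median time on drug | Primary cut | Follow-up cut | Rise |
|---|---|---|---|
| 6 months | 26.6% | 31.4% | 4.8 points |
| 10 months | 31.3% | 39.3% | 8.0 points |
| Nobody stops | 41.1% | 58.8% | 17.7 points |

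The hazard is the same in every cell. Mean exposure per patient rises from 5.5 to 7.1 months (ratio 1.28) with a 6-month median, from 6.6 to 9.3 (1.40) with a 10-month median, and from 9.0 to 15.0 (1.67) if nobody stops.

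**Against KD025-213.** The size cannot be computed, because its exposure is not reported. Two illustrations show what would follow from assumed differences:
- Accrual length. If one study enrolled over 12 months rather than 6, both cut 6 months after last enrolment and with the same λ, crude incidence would be 35% versus 31% (10-month median on drug) or 50% versus 41% (nobody stops).
- Exposure ratio k. Taking 1 − (1 − p)^k with k from 0.67 to 1.5, a reference value of 28.9% would appear as 20% to 40%, and 10.8% as 7% to 16%.

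**Sampling error for scale.** 6/30 = 20% has an exact 95% CI of 7.7% to 38.6%.

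**The case against.** The strongest case against runs as follows.

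- **A between-study difference is not shown.** A reader might infer that exposure differs between this trial and KD025-213, and so that crude percentages cannot speak to safety consistency. The documents do not support that. They give no KD025-213 exposure, and both primary cuts fall 6 months after last enrolment. This stands. What remains is that a shared cut rule does not equalise exposure: accrual length matters, and eligibility differs (1 to 5 prior lines here, at least 2 there), so time on drug may differ.
- **The calculated rise compares this trial's own cuts.** This also stands: it does not measure bias against KD025-213. The 18-point figure needs nobody to stop, which is unrealistic when KD025-208 had a median failure-free survival of 10.7 months.
- **Exposure is already reported.** True, and a careful reader can set the tables side by side. But an exposure table alone yields no AE rate.
- **The analysis is descriptive with 30 patients.** Sampling error will usually exceed the exposure effect. That limits the weight of the point. The effect is still systematic, and a larger sample would not remove it.
- **A rate has its own artefact.** Suppose 9 of 30 patients have a first event at 0.5 month, none occur later and nobody stops. Crude incidence is 30% at both cuts. Patient-months at risk are 9 × 0.5 + 21 × 9 = 193.5, then 9 × 0.5 + 21 × 15 = 319.5, so the rate falls from about 56 to 34 per 100 patient-years. Longer follow-up now looks safer. This is right, and is why the rate should only supplement the percentages.
- **Table 1 is background.** No section names it as the comparator; KD025-213 is named. This stands, and it is a reason to say explicitly which KD025-213 data will be used.

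**Conclusion.** The point holds as a cheap improvement in interpretation; it does not correct an error, and no stated figure is wrong. Both documents plan AEs only as crude subject percentages, although treatment is open-ended and safety consistency is a declared aim. Between the two cuts, an unchanged risk would appear about 5 to 8 points higher. That rests on a constant hazard giving 30% by 6 months, uniform 6-month enrolment and a median of 6 to 10 months on drug, all but the 6-month enrolment period being assumptions. Early-onset events would rise less. Any effect on the comparison with KD025-213 is possible, but its existence and size cannot be determined from the documents.

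**What to change.** Keep the crude percentages. In SAP 8.5.1, with a matching line in Protocol 10.6.3, add two summaries for any, related, serious and grade 3 or higher TEAEs, TEAEs leading to treatment discontinuation, and the infection, cytopenia and hepatic groupings:

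- (a) As a supplementary column, patients with a first event divided by patient-years at risk, with an exact Poisson 95% CI. Time at risk runs from first dose to first event or end of AE collection. The treatment duration in SAP 5.5 is therefore not itself the denominator, although the dates needed are already collected.
- (b) Incidence within the first 6 months from first dose, which does not assume a constant hazard.

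For the safety consistency statement, specify KD025-213 200 mg QD at the matched cut (6 months after last enrolment) rather than the pooled Table 1. Show both studies' exposure beside the AE table. Give (a) and (b) for KD025-213 where the originator can supply time at risk or onset dates. Do not rest the statement on the rate alone.

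Cost: a few extra columns, a data request to the originator that may not be met in full, and a rate that needs a footnote because it falls with longer follow-up when events occur early.
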